The main variable of interest and primary outcome measure of the treatment effect is the mucosal-plaque index (MPS). It consists of the sum of a four-point plaque score (PS) and a four-point mucosal score (MS). For the PS, score of 1 suggests no visible plaque, score of 2 suggests plaque is barely visible, score of 3 suggests a moderate amount of plaque, and score of 4 suggests large amount of plaque almost covering the whole surface of teeth. For the MS, score of 1 suggests normal mucosal, score of 2 suggests mild inflammation, score of 3 suggests medium inflammation, and score of 4 suggests strong inflammation. For both scores, if in doubt between 1 and 2, they are instructed to score 1. If in doubt between 3 and 4, they are instructed to score 4.

The index is designed to evaluate oral health and oral hygiene in groups of individuals, developed for use in institutions. This makes it a suitable index to be used when conditions are not optimal to assess the patient. In prison, dental staff have limited equipment and poor light compared to conditions at a dental clinic. It was therefore important to use an index designed to be used outside of dental clinics with less optimal conditions for oral examination.

The secondary measures of outcome are based on questionnaire responses. These are questions asked both prior to treatment and during the follow-up period, and measures changes in how the prisoner perceives his oral health, how his routines are for maintaining his teeth, and his intake of food and drinks. How these questions are formulated can be seen from the questionnaire directly. These questions are designed to measure behavioral changes because of the intervention. As the questions are identical at each meeting point, any difference in changes across the treatment and control group is likely to be a result of the intervention. Importantly, even though the MPS-index may not measure a significant change in oral hygiene, such behavioral changes may still be of great importance. For example, even though a prisoner does not change his cleaning routines and is unable to improve his plaque score, a reduction in intake of unhealthy food and drinks may still reduce the damage on his teeth. Likewise, an improved perception about their oral health, may still improve self-esteem, even though there is no reduction in plaque score.

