Prisoners are not informed whether they are in the treatment or control group and are therefore blind to treatment status. Dental staff are blind to prisoners' treatment status at the time of the first oral examination and questionnaire. The prisoner's treatment status is revealed just after this. Hence, dental staff collects all data prior to knowing the prisoner's treatment status, and only learn this when they start the MI-based conversation. When prisoners are back at T1 and T2 for follow-up oral examinations and questionnaires, dental staff might still remember whether the prisoner was treated or not. To partially account for potential bias in the oral examination (assessment of oral hygiene and inflammation in gingival), there are two independent assessments of this at T1 and T2. See pre-specification of analytical decisions for more on this.

Power calculations:

We have used GPower and Optimal Design to conduct power calculations.

GPower is used to calculate required sample size for simple comparison of means for the main variables of interest between the treatment and control group, without considering that data is collected at multiple sites. We choose the non-parametric Wilcoxon-Mann-Whitney test, set alpha to 0.05 and required power to 0.8. There is uncertainty concerning the effect size. Previous literature offers some guidance, however there are several important differences to our study. MI-interventions to change oral health have previously been tested on periodontist patients and patients with mental illness, populations that differ from ours. For our main variable of interest, level of plaque, these studies have found effect sizes ranging from 0.286 to 1.213¹. However, one should note that these studies have used different indexes to measure plaque, questioning the comparability of the effect sizes. Setting the power estimate to a moderate level in this range, to 0.5,

¹ An effect size of 0.286 was found after 12 weeks in Brand et al. (2012), whereas an effect size of 1.213 was found in Godard et al. (2011).

our required sample size is 106 prisoners. If we use a more conservative estimate and set it to the lowest effect size observed in the studies referred to above (0.286), the required sample size is 320.

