As mentioned under the section for blinding, there will be two assessments of the MPS index score at T1 and T2, as dental staff are not blind to their second and third meeting with the prisoner. If the original examiner finds no improvement in the MPS-index score, the second examiner's score will be ignored. If the original examiner finds an improvement, the average score of the original examiner and the second examiner will be used, however the second examiner's score will not be used to increase the average score above the assessment of the original examiner. We consider this a conservative approach. If the original examiner is not part of the team that evaluates at T1 and T2 (for example if the prisoner has been transferred to a different prison, or due to sick absence), an average score of the two assessments by the new examiners will be used.

Another concern is potential differences in how oral examinations and the intervention is conducted across multiple sites. To minimize differences, all dental staff have undergone the same MI training and practice. All oral examinations are being conducted by trained professionals, and they have gone through a calibration day prior to the start of the data collection. Moreover, they will continuously be provided guidance from a professional MI-consultant. In addition, we track the time they spend on each MI-based conversation.

Recruitment of prisoners may also be slightly different from one prison to another, as in half of the prisons it is done by prison officers and the other half it is done by dental staff. Prisoners may perceive the question of whether they want to participate or not differently, depending on whether they are asked by a prison officer compared to a dental staff. Moreover, the language assessment may also be different. Although this occurs independent of the randomization, it might lead to a difference in the population recruited to the experiment across prisons. Unfortunately, we could not have the same recruiter across all prisons. However, the information provided to the prisoners is the same across all prisons. This also applies to the instructions concerning language assessment; in the case of uncertainty about Norwegian language skills, the same screening question is asked across prisons, and the same evaluation criteria is being used.

Conclusion

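### The rule for combining the two examiners' MPS scores, as worded, can only confirm or enlarge an improvement, the opposite of the conservative safeguard it is said to be

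*Combined protocol and SAP*

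**What the plan says.** The *Blinding* section accepts that at follow-up "dental staff might still remember whether the prisoner was treated or not", and *Other issues* states that "dental staff are not blind to their second and third meeting with the prisoner". The remedy is two independent MPS assessments at T1 and T2, introduced with the words "To partially account for potential bias in the oral examination". *Other issues* then says how to combine them:

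- **Original examiner finds no improvement:** "If the original examiner finds no improvement in the MPS-index score, the second examiner's score will be ignored".
- **Original examiner finds an improvement:** the two scores are averaged, "however the second examiner's score will not be used to increase the average score above the assessment of the original examiner".
- **Original examiner absent:** "an average score of the two assessments by the new examiners will be used".

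Of the rule for the first two cases the plan says: "We consider this a conservative approach".

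*Treatment effects and measurements* defines MPS as a plaque score plus a mucosal score, each from 1 to 4. High is bad: for plaque, "score of 4 suggests large amount of plaque almost covering the whole surface of teeth". H1 predicts a reduction.

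**The concern.** A lower MPS is better. A cap that keeps the combined score from rising above the original examiner's score therefore blocks the second examiner from reducing a recorded improvement, but still lets that examiner enlarge it. That contradicts the claim that the rule is conservative, and it leaves little of the protection the second assessment was meant to give.

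The authors may have used *increase* to mean *make more favourable*. Reversing the cap removes that contradiction but leaves an asymmetry: the second score counts only if the original examiner, who may remember allocation, reports an improvement. A plain mean applies when that examiner is absent, so the primary outcome is scored by two different rules within one trial.

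At stake is the primary outcome at T1, the time point of main interest, and its main protection against unblinded scoring. The two readings also yield two different datasets from the same examinations, and a choice between them made after seeing results would not be pre-specified.

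**Working it through.** The plan gives no figure for this rule, so there is none to reproduce. The check has two parts.

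**1. Enumeration (no assumptions).** Let B be the T0 score, O the original examiner's follow-up score and S the second examiner's, each an integer from 2 to 8. Improvement means O < B.

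- As worded: O if O ≥ B, otherwise min(O, (O+S)/2).
- Likely intended: O if O ≥ B, otherwise max(O, (O+S)/2).

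| B, O, S | As worded | Intended | Plain mean |
|---|---|---|---|
| 6, 4, 6 | 4 | 5 | 5 |
| 6, 4, 2 | 3 | 4 | 3 |
| 6, 6, 8 | 6 | 6 | 7 |
| 6, 6, 4 | 6 | 6 | 5 |

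In the first row the wording discards a dissenting second score. In the second it enlarges the improvement from 2 points to 3. The last two rows show what both readings ignore: row 3 leaves lenient scoring uncorrected (in a treated prisoner this favours the intervention), and row 4 leaves harsh scoring uncorrected (in a control it does the same).

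There are 7 × 7 × 7 = 343 combinations.

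- O < B: 21 (B, O) pairs × 7 = 147. S < O in 35, S > O in 91, S = O in 21.
  - As worded, the second score lowers the result in 35 and raises it in 0.
  - On the intended reading, it raises the result in 91 and lowers it in 0.
  - The readings disagree in 35 + 91 = 126 of 147.
- O ≥ B: 28 pairs × 7 = 196. S is ignored on both readings. It differs from O in 28 × 6 = 168, and in 56 of the 196 the second examiner finds an improvement.

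These counts describe the rule; they are not frequencies in prisoners.

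**2. Simulation (all rater parameters assumed, because the plan gives none).** There is no true effect, and the original examiner is lenient to treated prisoners by 0.05, 0.1 or 0.2 latent SD. Plaque and mucosal scores are cut from latent normals at the 25th, 50th and 80th percentiles. The baseline–follow-up correlation is 0.75, examiner error SD is 0.3 or 0.6, and both arms improve by 0, 0.5 or 1.0 SD. Each scenario has 2,000,000 prisoners; shared-bias runs used 0.2.

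Share of the original examiner's bias left in the arm difference:

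| Second examiner | As worded | Intended | Plain mean | Second only |
|---|---|---|---|---|
| Unbiased | 84–98% | 73–83% | about 50% | about 0% |
| Half the bias | 91–101% | 87–92% | about 75% | about 50% |
| Same bias | about 95–106% under every rule | | | |

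Monte Carlo error of the share is about 2–3 points at bias 0.05 and under 1 point at 0.2.

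Illustrative false-positive rates (two-sided 0.05, tie-corrected Mann-Whitney, 4,000 trials each, at the sample sizes in *Power calculations*):

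| N, bias | As worded | Intended | Plain mean |
|---|---|---|---|
| 320, 0.05 | 7–8% | 6–7% | about 6% |
| 320, 0.1 | 14–19% | 10–15% | 8–9% |
| 320, 0.2 | 36–57% | 25–43% | 15–21% |
| 106, 0.2 | 16–22% | 12–17% | 9–10% |

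With no rater bias every rule holds about 5%.

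A second, simpler simulation on the MPS scale (examiner error SD 0.7, unbiased second examiner, no true effect) had the original examiner score controls 0.3 too high. The arm difference was −0.29 as worded, −0.25 on the intended reading, −0.15 with a plain mean and 0.00 with the second examiner alone.

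**The case against.** The strongest reply is that the authors plainly meant the reverse cap, since they call the rule conservative in the next sentence. On that reading the rule can only shrink a prisoner's improvement, and the largest figures above do not apply. This is a fair guess at intent, but the text as written instructs the opposite, and the intended rule still discards the second score in the no-improvement branch.

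Second, the rule applies to both arms, so enlarging individual improvements need not enlarge the treatment effect. This stands. With no rater bias and a true effect of 0.5 in the simpler simulation, the arm difference was −0.475 from the original examiner alone and −0.493 as worded, about 4% larger. Material harm needs scoring that depends on allocation, a possibility the plan raises but does not quantify.

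Third, the plan promises only a partial correction, and even the literal rule usually removes a little bias when the second examiner is unbiased. So the clear contradiction is with the claim of conservatism; against the stated aim the rule is weak rather than contrary.

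Fourth, the enumeration weights all combinations equally, and 49 of the 196 no-improvement combinations have T0 = 2, where improvement is impossible. This is correct, and the counts are used only to show what the rule can do.

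Fifth, the exception for an absent examiner is openly pre-specified, and a plain mean is itself a compromise because it keeps about half the bias. Both are true. The exception does show that the plan already accepts the simpler rule.

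**Conclusion.** The concern holds. That the wording runs against its stated purpose follows from the scale and the clause alone: 0 combinations in which the second score tempers an improvement, and 35 in which it enlarges one. On the likely intended reading the rule is conservative for an individual's improvement, but not dependably so for the comparison between arms.

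The size of the harm rests on assumed rater parameters. With an unbiased second examiner, the ordering in both simulations was the same: most bias kept as worded, less on the intended reading, about half with a plain mean. If the second examiner fully shares the bias, no combining rule helps. Settling the wording before analysis is essential, because the choice of reading changes the primary-outcome value in 126 of the 147 combinations where the original examiner finds an improvement. The preference for a plain mean is a recommendation that rests on the simulations and on the plan's own exception.

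**What to change.** In *Other issues*, delete the clause that ignores the second score and the clause that caps the average. Replace both with the unconditional mean of the two T1 or T2 assessments, for every prisoner in both arms, whether or not improvement was found. Keep the second score on record in every case.

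Add a sensitivity analysis. Where the original examiner took part, use the score of the examiner who did not conduct the T0 session; where both examiners are new, keep their mean. Record and report whether that examiner knew the allocation, because the gain depends on freedom from the same bias.

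The cost is SAP wording and one extra recorded item, since both assessments are already planned. Any apparent benefit may become somewhat smaller, and the mean still keeps about half of the original examiner's bias. The single score in the sensitivity analysis is noisier: in the simulation its SD was 1.45–1.52 against 1.38–1.39 for the mean, about 4–10% larger. According to its *Conclusion*, the plan was written before any data analysis. The change should likewise be dated and made before outcome data are examined by arm.
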